6.5 Long term Follow up after 6 months

After the 6 month visit, subjects must be evaluated at the Clinical Center (12 months +/- 2 month) and then yearly (+/- 2 month) thereafter for 5 years and have blood work done as detailed below. Subjects will be seen by their home physician as clinically indicated and the Clinical Center and home physician will continue to communicate.

- Complete blood counts with differential (annually +/- 2 month)
- Chem 20 (annually +/- 2 month)
- Reticulocyte counts (annually +/- 2 month)
- Flow cytometry of the peripheral blood (annually +/- 2 month)
- EBV and CMV PCR in the blood (at 12 months only +/- 2 month)
- Thyroid function tests (annually +/- 2 month)
- Bone marrow biopsy and aspiration with cytogenetics (at 12 months +/- 2 month and annually thereafter, as clinically indicated)

7 ANCILLARY LABORATORY RESEARCH STUDIES

7.1 Collection of samples: During the course of participating on this study, blood and tissue may be collected for correlative laboratory research studies as follows:

- Peripheral blood: 60 cc of blood (at baseline), 20 cc of blood (with EBV/CMV monitoring, at 3mo, 6 mo and annually thereafter (repeated in the event of a 2nd cycle),
- Bone marrow aspirate: 5 -15 cc of bone marrow aspirate (baseline, 6 months, 12 months, and annually thereafter.

- Apheresis: One apheresis collection of approximately 10^{10} leukocytes in a volume of 200 ml prior to initiation of Campath and a repeat apheresis procedure when there is evidence of lymphocyte recovery.

7.2 Intended use: These specimens will not be read by a pathologist or used for diagnostic purposes. The studies will not be used in assessing the primary endpoint but are undertaken for descriptive or exploratory ancillary research. These ancillary studies may be done and if done, may be correlated with the presence or absence of response to protocol therapy:

- Characterize LGL cells on a molecular level using gene expression profiling and T-cell receptor genotyping.
- Characterize clonal expansions in LGL by V-beta profile and/or TCR-beta chain sequencing in the peripheral blood and/or bone marrow; identify the epitope by using PS-SCL.
- Flow cytometric analysis of lymphocyte subsets
- Measurement of lymphocyte function and immune response directed to EBV and CMV
- Chromosome analysis using standard cytogenetics and FISH
- Analysis of the T cell receptor V-beta profile in the marrow and peripheral blood of responders and non-responders.
- Clonality analysis using X-chromosome gene inactivation analysis
- HLA typing to see if HLA type correlates with response.
- Evaluation for the presence of abnormalities of the telomere complex
- Assay for cytokines/chemokines and their receptors
- Serum (or plasma) and cells for viral analysis
- Hematopoietic progenitor colony formation and long term-culture-initiating cell assays
- Serum (or plasma) and cells for DNA/RNA extraction and PCR for viral nucleic acids

Campath specific studies that may be done include:

- Anti-alemtuzumab (Campath®) antibody
- Serum levels alemtuzumab (Campath®) may be measured after the last dose and after 1 month from completing the infusion. If done, The alemtuzumab (Campath®) assays will be sent for batch processing to the laboratory of [name], BioAnaLab Limited, [name]. There is a human Material Transfer Agreement (MTA) executed between Cardiff University and NHLBI. This MTA is to send PBMC for the identification of targets (antigens) recognized by LGL clone. No transfer of

material will be accomplished until a Material Transfer Agreement is fully executed through the NHLBI Office of Technology Transfer and Development (OTTAD).

In the event there is sample left over, with the subject's permission, they will be stored for other exploratory laboratory research studies previously reviewed and approved by the NHLBI as listed in Appendix A.

- 7.3 Storage:** Research samples will be stored with identifiers in the secure laboratory of the principal investigator.
- 7.4 Tracking:** Samples will be ordered and tracked through the CRIS Research Screens. Should a CRIS screen not be available, the NIH form 2803-1 will be completed and will accompany the specimen and be filed in the medical record. Specimens will be entered in the NHLBI Biospecimen Inventory System (BSI). Samples will not be sent outside NIH without IRB notification and an executed MTA.
- 7.5 End of study procedures:** Samples from consenting subjects will be stored until they are no longer of scientific value or if a subject withdraws consent for their continued use, at which time they will be destroyed.
- 7.6 Loss or destruction of samples:** Should we become aware that a major breach in our plan for tracking and storage of samples has occurred, the IRB will be notified.
- 7.7 Technology Transfer**

This protocol has no associated patents, CRADAs or CTAs. If done, the alemtuzumab (Campath®) assays will be sent for batch processing to the laboratory of [name], BioAnaLab Limited, [name]. There is a human MTA executed between Cardiff University and NHLBI. No transfer of material will be accomplished until a Material Transfer Agreement is fully executed through the NHLBI Office of Technology Transfer and Development (OTTAD).

8 BIOSTATISTICAL CONSIDERATIONS

8.1 Primary Endpoint

The primary endpoint is hematologic response measured at 3 months after first dose alemtuzumab (Campath®) sustained on at least two serial measurements performed 1 week apart and sustained for 1 month or more without support of exogenous growth factors or transfusions.

Complete Hematologic Response: normalization of all affected cell lines

Partial Hematologic Response: Improvement in one or more of the listed parameter (a, b, c) but not sufficient to achieve a complete hematologic response

a) ANC : a 100% increase in ANC to an ANC > 500 / μ L

b) Platelets:

For baseline platelet count $\geq 20,000 /\mu\text{L}$ but $\leq 50,000/\mu\text{L}$: a 100% increase in platelet count to a platelet count $> 50,000 /\mu\text{L}$

For baseline platelet count $< 20,000 /\mu\text{L}$: a 100% increase in platelet count to a platelet count $> 20,000 /\mu\text{L}$

c) Hemoglobin: Any increase in hemoglobin by 2 g/dl

8.2 Secondary Endpoints

8.2.1 Transfusion-Independence for red blood cells and/or platelets

8.2.2 Overall survival. In comparing the probabilities of survival between responders and non-responders, the baseline time is set to be 3 months after first dose alemtuzumab at which response is determined for the primary endpoint.

8.2.3 Life Threatening Toxicity. Subjects who do not complete the treatment course because of toxicity or voluntary withdrawal will be included in analyses.

8.2.4 Relapse-free survival is defined as the time elapsed between time of documented response to Campath and evidence for relapse. Relapse is defined as a fall in peripheral blood counts to 50% the values obtained during the response period.

8.2.5 Molecular Response to Campath is defined as disappearance of the clonal population of T-LGL

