2.4 Scientific and Clinical Justification

Mature post-thymic T-cell malignancies are a heterogeneous group of rare lymphoid disorders which include T-prolymphocytic leukemia, cutaneous T-cell lymphoma, T-LGL leukemia, and human T-cell lymphotropic virus associated with adult T-cell leukemia-lymphoma. These diseases are often resistant to conventional chemotherapeutic regimens and relapses are common, resulting in patients becoming refractory to treatment. Campath has shown to be active in T-cell malignancies⁵⁰. Anecdotal reports of successful treatment with Campath in patients with T-LGL leukemia refractory to immunosuppression are emerging in the literature^{51,52,53}. An illustrative case was that of a 53-year old woman with T-LGL who was treated with a succession of multiple immunosuppressive and/or chemotherapeutic regimens over 20 months which included methotrexate, prednisone, cyclosporine, cyclophosphamide, anti-thymocyte globulin, OKT3 and pentostatin with no significant sustained response⁵². Following treatment with Campath, she experienced sustained improvement of the blood counts with minimal toxicity.

Although T-LGL leukemia is commonly thought of as an indolent disease, a majority of patients end up requiring treatment due to constitutional symptoms or complications of cytopenias such as fatigue, bleeding and/or infections⁵⁴. The T-LGL CD3+ clone is frequently resistant to chemotherapeutic agents, and immunosuppression remains the mainstay of therapy. Although small case series indicate that responses are achieved with immunosuppressive agents such as corticosteroids, methotrexate, cyclophosphamide and cyclosporine; relapses are common, and discontinuation of drug and/or long-term intermittent use is often required. This practice often leads to significant toxicity in older patients, which is the age group where T-LGL is most commonly observed. The long term use of alkylating agents such as cyclophosphamide also raises the potential for clonal disorders such as myelodysplasia and leukemia. In addition, eradication of the T-LGL CD3+ clone is infrequent. Campath is a potent lymphocytotoxic agent which is currently approved for the treatment of CLL. The use of Campath in T-LGL may not only improve the cytopenia(s), but also eradicate the leukemic clone and result in more prolonged remission and/or decrease in the rate of relapse.

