4. ELIGIBILITY ASSESSMENT

4.1 Inclusion Criteria

4.1.1 Clinical history supportive of the diagnosis of T-LGL leukemia (i.e. a history of cytopenias with

peripheral blood morphologic evidence of LGLs)

4.1.2 Immunophenotypic studies of peripheral blood showing an increased population of T-LGLs (suggested by staining with CD3+, CD8+ and CD16+ or CD57+) or gamma-delta T cells.

4.1.3 Restricted or clonal rearrangement of the T-cell receptor by PCR **AND one or more of the following**

Severe neutropenia (< 500 neutrophils/ μ L);

OR

Severe thrombocytopenia (< 20,000 platelets/ μ L), or moderate thrombocytopenia (< 50,000 platelets/ μ L) with active bleeding;

OR

Symptomatic anemia with a hemoglobin < 9 g/dL or red blood cell transfusion requirement of > 2 units/month for two months prior to initiation of Campath

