8.4 Statistical Methods

The planned analyses will include descriptive statistics on the proportions of responses (i.e. % subjects with partial or complete response) and the time to response. The response probabilities will be estimated using the sample proportions and their inferences including confidence intervals and hypotheses testing will be evaluated using Binomial distributions.

The time to responses and the relapse-free survival will be analyzed using appropriate tools in survival analysis, such as cumulative incidence estimate and Cox regression type analysis for covariates, which takes into consideration both death without the event of interest as a complete risk and random censoring due to loss of follow-up. The Kaplan-Meier estimates and Cox regression will be used to evaluate the treatment effects on the overall survival. Graphical tools will be used to display the appropriate estimates (i.e. estimated proportions, the cumulative incidence curves, Kaplan-Meier curves) and their corresponding 95% confidence intervals.

Methods based on multiple regression, analysis of variance, and logistic regression will also be employed if deemed appropriate.

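### For hemoglobin responders, the relapse level in section 8.2.4 lies below baseline unless hemoglobin has doubled, so a fully lost response can still count as relapse-free

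*Combined protocol and SAP*

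**What the plan says.** Section 8.2.4 measures relapse-free survival from documented response to relapse and defines the event once for all counts: "Relapse is defined as a fall in peripheral blood counts to 50% the values obtained during the response period". It does not refer to baseline, to loss of the section 8.1 criterion or to transfusion. It also does not say which response-period value is halved, or whether one lineage is enough.

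Section 8.1 sets the partial-response criteria by lineage. Hemoglobin has an absolute criterion: "c) Hemoglobin: Any increase in hemoglobin by 2 g/dl". ANC needs a doubling as well as a floor: "a 100% increase in ANC to an ANC > 500". Platelets likewise need a doubling, past 20,000 or 50,000 per μL depending on baseline. Any response must be "sustained for 1 month or more without support of exogenous growth factors or transfusions".

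Section 4.1.3 admits subjects on anemia alone: "Symptomatic anemia with a hemoglobin < 9 g/dL or red blood cell transfusion requirement of > 2 units/month for two months". Section 8.4 analyses relapse-free survival with survival tools "such as cumulative incidence estimate and Cox regression type analysis for covariates" and does not redefine relapse. Section 5.2 makes relapse one of the conditions for a discretionary second cycle and has no definition of its own.

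**The concern.** A relapse rule should be able to recognise that the response has gone. Halving the response value does this where response means at least a doubling. Hemoglobin response means a gain of 2 g/dL on a baseline that is usually several times larger, so half the response value can lie well under the starting point. A subject with baseline 8 g/dL who responds and then returns to 8 is again below the 9 g/dL entry level, yet has not relapsed under section 8.2.4. Resumed red cell transfusion is not an event either, and it can hold hemoglobin above the 50% level.

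Durability is at stake. Section 2.4 gives as a reason for the study that Campath may "result in more prolonged remission and/or decrease in the rate of relapse", and relapse-free survival is the endpoint that speaks to this.

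**Working it through.** The plan gives no figure to reproduce here; the check is algebra on its definitions.

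**Inputs.** Baseline b; gain g of at least 2 g/dL for hemoglobin (8.1(c)); response value R = b + g; relapse level 0.5R (8.2.4). Anemia entry on hemoglobin level requires b below 9 g/dL (4.1.3).

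**Condition.** Relapse level = (b + g)/2. This is below b if and only if g < b, that is, R < 2b. The gap below baseline is b − (b + g)/2 = (b − g)/2.

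**Hemoglobin (g/dL): relapse level, with distance below baseline in brackets.**

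| Baseline | Gain 2 | Gain 4 | Gain 6 |
|---|---|---|---|
| 6 | 4.0 (2.0) | 5.0 (1.0) | 6.0 (0) |
| 7 | 4.5 (2.5) | 5.5 (1.5) | 6.5 (0.5) |
| 8 | 5.0 (3.0) | 6.0 (2.0) | 7.0 (1.0) |
| 8.9 | 5.45 (3.45) | 6.45 (2.45) | 7.45 (1.45) |

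For the relapse level to reach baseline, response hemoglobin would have to be 2b: 12, 14, 16 and 17.8 g/dL for the four rows.

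**ANC and platelets, partial response.** Doubling gives R ≥ 2b, hence 0.5R ≥ b. At the minimum qualifying response:
- ANC 400 to 800 gives relapse at 400, equal to baseline.
- ANC 100 to 501 gives 250.5, above baseline.
- Platelets 30,000 to 60,000 give 30,000, equal to baseline.

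Among the partial-response criteria, the fault is confined to hemoglobin.

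**The opposite error.** ANC rising from 300 to 4,000 and falling to 2,000 is a relapse (0.5 × 4,000 = 2,000). Yet 2,000 is more than twice 300 and above 500, so 8.1(a) is still met.

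**Scale, on assumptions only.** Let h be the share of responders who respond in hemoglobin alone, and r the share of those who lose the response without reaching the 50% level. Ignoring censoring and competing death, relapse incidence is understated by h × r. The documents give neither figure. Assuming h of 10% to 30% and r of 20% to 50%, the range is 0.10 × 0.20 = 2 points to 0.30 × 0.50 = 15 points. With 39 subjects and the hypothesised 50% response there are about 20 responders, so this is about 0.4 to 3 subjects.

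**The case against.** The algebra is hard to dispute, so the case on the other side concerns reading and reach.

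- *Half of the gain was meant.* That would put relapse at 9.0 g/dL for 8 to 10 and remove the problem. But the text halves the values themselves. If the gain was meant, the text still needs correcting.
- *Another lineage would catch the loss.* This may hold for a subject who also responded in ANC or platelets, if one lineage suffices. It cannot hold for a subject who responded in hemoglobin alone.
- *Transfusion independence (8.2.1) and 6-month response (8.2.6) cover it.* They may show some lost responses, but they do not feed relapse-free survival, and a 6-month assessment cannot show later loss.
- *Some of these subjects will leave the study.* Under section 8.6, starting certain other immunosuppression is an off-study criterion, so some may be censored and not carried as relapse-free. This stands and reduces the reach.
- *The numbers are small.* This stands. Section 2.1 says anemia is less frequent than neutropenia. The 95% interval for a proportion of 50% in 20 subjects is about ±22 points, wider than any bias in the assumed range.
- *Changing the definition after relapses have been seen is itself a risk.* This stands. Section 2.5 reports signs of relapse in some patients, so an amended definition should stand beside the present one and not displace it.

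A reader might also infer that complete responses share the fault, since "Complete Hematologic Response: normalization of all affected cell lines" does not require doubling. For hemoglobin the formula above applies whether the response is partial or complete. For mildly reduced ANC or platelets the extension rests on normal limits, and on a definition of an affected line, that the documents do not give.

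**Conclusion.** The point holds for subjects whose response rests on hemoglobin and whose hemoglobin has not doubled. The whole gain can be lost, or red cell transfusion resumed, without a relapse event, and relapse-free survival in this group is biased upward. This follows from sections 8.1 and 8.2.4 alone, and no other section cures it.

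A reader might infer that relapse-free survival is overstated for the trial as a whole, or by some definite number of points. The documents support neither. The number of hemoglobin responders is not given, the 2 to 15 point range rests entirely on assumed shares, and the same rule can call relapse too readily in ANC, so the net direction is not shown. Nor do the documents support an effect on the trial's decisions: the endpoint is secondary and has no decision rule, and the primary endpoint and stopping rules do not use it. Severity is minor to moderate.

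**What to change.** For the analysis of relapse-free survival only, extend section 8.2.4 so that relapse in a responding lineage also occurs on either of these:

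1. Return to or below the baseline used for the section 8.1 response, confirmed on a repeat count where one is available and dated to the first.
2. For hemoglobin responders, resumed red cell transfusion for recurrent anemia. Transfusion for surgery or unrelated bleeding does not count; section 5.4 permits transfusion as clinically needed.

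State which response-period value the 50% refers to (first, mean or peak, for example) and whether one lineage is enough. Report the definition as now written and the extended one side by side, and disclose the date of the change.

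A baseline floor is steadier than counting any loss of the 2 g/dL gain. Assume a stable true hemoglobin of 10.0, baseline 8, and independent normal variation with SD 0.3 to 0.8 g/dL. A single count then falls below 10.0 with probability 0.50, but to 8.0 or lower with probability at most 0.0062. The floor changes nothing for ANC and platelet partial responders.

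Costs:
- Earlier responders need some re-adjudication from existing counts and progress notes, because the visit schedules do not itemise transfusions.
- After 6 months scheduled counts are annual (6.5), so dating is coarse and confirmation may depend on unscheduled counts.
- Reported durability may be less favourable.
- The ANC over-call remains, and a partial loss that stays above baseline (10 to 8.5 from baseline 8) is still not a relapse.

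Section 5.2 relies on relapse without defining it, so sections 8.1, 8.2.4 and 5.2 must be reconciled. No retreatment rule is proposed here.

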5.4 Permitted supportive care

- Transfusional supportive care (e.g., blood and platelets) as clinically indicated.
- Growth factors if deemed necessary by the investigator or treating physician

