8.6 Off study criteria

Per Subject choice: Subjects may be removed from study at their request. The risks of withdrawing will be discussed, as will alternative treatment options.

Per principal investigator decision: Alemtuzumab (Campath®) administration will be discontinued; the subject will be followed until the event has resolved if the subject develops:

- Intolerance of alemtuzumab (Campath®) infusion as manifested by hypotension, fever, chills and/or rash that is refractory to supportive measures; OR any subject who develops CTCAE grade 4 hepatic injury or DIC subsequent to infusions of alemtuzumab.
- Life threatening acute hypersensitivity reactions
- Pregnancy or unwillingness to refrain from pregnancy
- Initiation of additional immunosuppressive therapy (except steroids or CsA)
- Failure to respond to Campath therapy
- Subject non-compliance
- Lost to follow-up

- Study completion

Those subjects who choose to withdraw or are removed from the study per PI decision will be asked to continue to have labs monitored through the 6 month off drug time point so that we can continue to monitor for post Campath related safety issues. Once off study subjects will be referred back to his or her referring physician or consented to the Hematology Branch evaluation and treatment protocol (94-H-0010) for consideration for standard therapy or evaluation for eligibility for another branch protocol, depending on what is considered to be in the best interest of the subject.

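### Response must be free of growth factors and transfusions, but relapse is judged on counts alone, so resumed support can hide or delay relapse and lengthen relapse-free survival

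*Combined protocol and SAP*

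**What the plan says.** Section 8.1 defines the primary endpoint as haematologic response at 3 months, confirmed on serial measurements and "sustained for 1 month or more without support of exogenous growth factors or transfusions".

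Section 8.2.4 sets the durability endpoint: "Relapse-free survival is defined as the time elapsed between time of documented response to Campath and evidence for relapse". The next sentence gives the event: "Relapse is defined as a fall in peripheral blood counts to 50% the values obtained during the response period". It does not mention support.

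Section 5.4 permits "Transfusional supportive care (e.g., blood and platelets) as clinically indicated" and "Growth factors if deemed necessary by the investigator or treating physician". It sets no time limit and makes no link to response or relapse status.

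Section 8.4 plans cumulative incidence and Cox-type analyses of relapse-free survival in a way that "takes into consideration both death without the event of interest as a complete risk and random censoring due to loss of follow-up". Resumed support is not among the events handled. Section 8.6 lists new immunosuppression, other than steroids or ciclosporin, as an off-study ground, but not growth factors or transfusions. Transfusion-independence is a separate secondary endpoint (8.2.1) with no stated definition.

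**The concern.** Support decides who enters the response state but plays no part in who leaves it. Once a responder is back on growth factor or transfusion, the recorded count reflects the support as well as the disease, and 8.2.4 still reads that count as continued response.

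Durability is part of the case for the trial. Section 2.4 hopes for longer remission or fewer relapses than with agents that need continued or intermittent use, and Section 2.2 lists G-CSF among the treatments that have given limited responses in this disease. If counts held up by restarted G-CSF or transfusion are credited to alemtuzumab, relapse-free survival measures the drug and the rescue together.

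The visit schedule adds to this. After 6 months, Section 6.5 requires blood counts only once a year. A scheduled count taken on support could be the only protocol-required count that year.

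**Working it through.** **1. The plan's own figures.** The documents state no figure for relapse-free survival, so there is none to reproduce. The one design figure is the Simon minimax design in 8.3 (6/19, then 16/39; 30% versus 50%). With X1 ~ Bin(19, p) and X2 ~ Bin(20, p), the probability of rejecting the null is the sum over x = 7 to 19 of P(X1 = x) × P(X2 ≥ 17 − x). This gives 0.0455 at p = 0.30 and 0.8036 at p = 0.50, and a search confirms n = 39 as minimax. Nothing in 8.2.4 enters this calculation.

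**2. The sections side by side.**

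| Section | Treatment of growth factors and transfusions |
|---|---|
| 8.1 response | Must be absent |
| 5.4 supportive care | Allowed on clinical judgement, no time limit |
| 8.2.4 relapse | Not mentioned; counts only |
| 8.4 analysis | Only death without the event and loss to follow-up are handled |
| 8.6 off study | Not a ground |
| 8.2.1 transfusion-independence | Transfusions only; does not feed into 8.2.4 |

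No section adds a support criterion to relapse.

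**3. Can support plausibly resume before the event?** Relapse level = 0.5 × response value. Compare it with the entry thresholds in 4.1.3.

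- Haemoglobin: entry at 8.9 g/dL plus the 2 g/dL response increment = 10.9; 0.5 × 10.9 = 5.45 g/dL. Response values of 10, 12 and 13 give 5.0, 6.0 and 6.5. The entry threshold is below 9 g/dL with symptoms.
- Platelets: response at 51,000/µL gives 25,500; response at 21,000 gives 10,500. The entry thresholds are below 20,000, or below 50,000 with active bleeding.
- Neutrophils: response at 501/µL gives 250.5; response at 1,000 gives 500. The entry threshold is below 500.

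In general the relapse level lies below an entry threshold E whenever the response value is below 2E. That is 2 × 9 = 18 g/dL for haemoglobin, 2 × 500 = 1,000/µL for neutrophils, and 2 × 20,000 = 40,000/µL for platelets (2 × 50,000 = 100,000 under the bleeding criterion). In these ranges a subject can again meet the entry level, and be given support, with no relapse event.

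**4. Size, by assumption only.** Let q be the true proportion of responders who relapse and f the fraction of relapses that support masks. Ignoring censoring, the apparent relapse-free proportion is 1 − q(1 − f).

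| q | True | f = 25% | f = 50% | f = 100% |
|---|---|---|---|---|
| 30% | 70% | 77.5% | 85% | 100% |
| 50% | 50% | 62.5% | 75% | 100% |

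With 17 responders, the fewest that reject the null at the final analysis, one masked relapse moves the proportion by 1/17 = 5.9 percentage points. The documents give neither q nor f.

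**The case against.** The strongest reply is that this is a secondary endpoint in a single-arm pilot, with no comparator, hypothesis or decision rule attached, and that renewed transfusion need would show up under 8.2.1. Both points stand and limit the consequence. But 8.2.1 does not cover growth factors and would not change the relapse-free survival estimate. It could also be said that 8.2.4 speaks of evidence for relapse, which leaves room for judgement; the sentence that follows closes that room by defining relapse through counts.

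A rule that made every restart an event would bias the other way. Perioperative transfusion, acute infection, or cytopenia caused by a second cycle could be miscounted as relapse. That is right, and the definition needs an exception.

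Four stronger readings are tempting but not supported:

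- A reader might infer a fixed inflation, such as 15 to 30 percentage points, by supposing that 15% to 30% of responders resume support before the counts halve. That only restates the supposition. It also needs every restart to be a true relapse and support to hold the count throughout follow-up; otherwise events are delayed, not lost.
- A reader might point to a responder whose neutrophils fall from 1,500 to 800/µL and who restarts G-CSF. A count of 800 is above the relapse level of 750, the response level and the entry level, and nothing suggests that support would be judged necessary there.
- A reader might say that support is unrestricted. Section 5.4 ties it to clinical indication or perceived need.
- A reader might say that anyone back on support no longer meets 8.1. Section 8.1 defines attaining response at 3 months, not a continuing status. The defect is that no section carries the support condition forward.

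**Conclusion.** The point holds as a flaw in the definition of a named secondary endpoint. Followed as written, 8.2.4 misses or late-dates relapse in a responder whose disease returns and who resumes support before the counts halve. The direction is firm for such subjects: durability is overstated. It does not extend to support given for an unrelated cause.

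The overstatement cannot be quantified from the documents; the table of q and f shows sensitivity only and is not an estimate. The 3-month response, its error rates and the sample size are unchanged. The definition should be corrected before relapse-free survival is analysed, but the point does not threaten the main result.

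**What to change.** Add to 8.2.4, labelled as an analysis definition so that the use of relapse for retreatment in 5.2 and the supportive care in 5.4 stay as they are:

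> For the relapse-free survival analysis, resumption of growth factor, or of red-cell or platelet transfusion, for the lineage that responded is a relapse event dated at its start, unless documented as short-term support for a cause other than return of disease (e.g. surgery, acute infection, or transient cytopenia from a second cycle). Counts obtained on support are not used to show continued response.

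State in 8.2.6 that response at 6 months uses the support-free condition of 8.1. Report relapse-free survival under the counts-only definition as a sensitivity analysis, so that readers can see how much the definition matters.

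The cost is modest but not nil. Relapse-free survival will look somewhat shorter, and someone must judge the cause of each restart. Section 9.3 already has data abstracted from Clinical Center and home-physician notes. Faxing of home-physician notes is specified only to 6 months (6.3, 6.4), however, and 6.5 then relies on general communication. Start dates of growth factor and transfusion after 6 months would have to be abstracted from those notes deliberately.
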